**Table 9. Stopping boundaries for CRc rate**

Stop accrual if the number with overall response is less than or equal to indicated (i.e., # patients with overall response) among the number of patients evaluated			
Number of patients evaluated for CRc	5	10-15	20
Number of patients with CRc (i.e., CR, CRp, or CRi) is less than or equal to	Never stop with this many patients	0	Always stop with this many patients

The monitoring rule for the toxicity rate, based on these assumptions and monitoring conditions above is found in **Table 10**. For example, accrual will cease if 4 or more patients experience toxicities among the first 5 patients.

**Table 10. Stopping boundaries for Toxicity**

Stop accrual if the number of drug-related non-hematological grade 3/4 toxicities is greater than or equal to indicated (i.e., # patients with toxicities) among the number of patients evaluated				
# patients evaluated	5	10	15	20
# patients with toxicities	4-5	5-10	7-15	Always stop with this many patients

Multc Lean Desktop (version 2.1.0) was used to generate the toxicity and futility stopping boundaries and the OC table (Table 11). In order to utilize the software for the design, a 10.0% ORR and beta (0.2, 1.8) priors were assumed for the standard treatment response distribution and experimental treatment response prior distribution, respectively. In addition, a 30% toxicity constant rate and beta (0.6, 1.4) priors were assumed for the standard treatment toxicity constant rate and experimental treatment toxicity prior distribution, respectively.

The probability of stopping the study early if the true ORR of the combination treatment was 30% and the true toxicity rate was 20% was 28.2%. Probabilities of stopping early for high true toxicity rates (i.e., 50%) were 77.8% when the true ORR was 20% and 75.8% when true ORR rate was 30%.

**Table 11. Operating characteristics for simultaneous monitoring response and toxicity rates for patients treated with combination treatment**

True Toxicity Rate	True ORR	Prob(stop the trial early)
--------------------	----------	----------------------------

Table 11. Operating characteristics for simultaneous monitoring response and toxicity rates for patients treated with combination treatment		
True Toxicity Rate	True ORR	Prob(stop the trial early)
0.10	0.10	0.3500
	0.15	0.1985
	0.20	0.1092
	0.25	0.0582
	0.30	0.0302
0.20	0.10	0.3756
	0.15	0.2301
	0.20	0.1443
	0.25	0.0953
	0.30	0.0684
0.30	0.10	0.4761
	0.15	0.3540
	0.20	0.2820
	0.25	0.2410
	0.30	0.2184
0.40	0.10	0.6552
	0.15	0.5748
	0.20	0.5274
	0.25	0.5004
	0.30	0.4855
0.50	0.10	0.8381
	0.15	0.8003
	0.20	0.7781
	0.25	0.7654
	0.30	0.7584

### 11.3 Statistical Analysis Plan

All patients who received any dose of the study agent will be included in the analysis for efficacy and safety. Demographic/clinical characteristics (including duration of response) and safety data of the patients will be summarized using descriptive statistics such as mean, standard deviation, median and range. For the primary efficacy analysis, we will estimate the ORR for the combination treatment, along with the 95% confidence interval. In addition, we will estimate composite CRc rate, partial response and marrow clearance rate within 3 months by FLT3 mutation. Patients who drop out of the study before completing all the cycles will be treated as “failures” for the primary analysis. ORR during the study period will also be presented with the 95% confidence interval. The association between ORR and patient’s clinical characteristics will be examined by Wilcoxon’s rank sum test or Fisher’s exact test, as appropriate. Toxicity type, severity and attribution will be summarized for each patient using frequency tables.

The distribution of time-to-event endpoints (DFS and OS) including overall survival and progression free survival will be estimated using the method of Kaplan and Meier. Comparisons of time-to-event endpoints by important subgroups will be made using the log-rank tests. Paired t-tests will be used to determine the immunological and molecular changes in the peripheral blood and bone marrow from baseline to the time of response, and to the time of disease progression.

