#### **Phase II**

1. To determine the composite CR (CRc) rate including CR (complete remission) + CRp (complete remission with incomplete platelet recovery) + CRi (complete remission with incomplete count recovery) within 3 months of treatment initiation in FLT3-ITD and –D835 mutated patients with relapsed/refractory AML.

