## 11.2 Phase II

The primary objective of the phase II is to evaluate the efficacy of the combination. The study has two cohorts (maximum of 20 patients for each cohort): (1) FLT3-ITD and –D835 mutated relapsed/refractory AML previously exposed to any FLT3 inhibitor, and (2) FLT3-ITD and –D835 mutated relapsed/refractory AML with no prior exposure to any FLT3 inhibitor.

For all the cohorts, the primary endpoint is the achievement of CRc (CRc=CR/CRp/CRi) at any time during the first three cycles of therapy and toxicity assessed at the end of one cycle of therapy. CRc and toxicity will be monitored simultaneously using the Bayesian approach of Thall, Simon, Estey (1995, 1996) and the extension by Thall and Sung (1998) separately for each cohort. Multic Lean Desktop (version 2.1) was used to generate the stopping boundaries and the OC tables for futility and toxicity monitoring.

- **Cohort #1: Patients with relapse FLT3-ITD and –D835 mutant AML (FLT3 inhibitor naïve cohort):**

The historical data suggested a CRc rate of 20% for this population and the target CRc with selinexor and sorafenib combination is 35%. The treatment will be considered worthy of further investigation if it elicits an increase in CRc to 35% with acceptable toxicity. A >30% therapy related non-hematological grade 3/4 toxicity rate is considered unacceptable. Given this, we will stop enrollment into this cohort if the observed patients' data suggest that:

- 1)  $\Pr(\text{CR}_{cE} > \text{CR}_{cH} + 0.15 | \text{data}) < 0.025$  or
- 2)  $\Pr(\text{TOX}_E > 0.30 | \text{data}) > 0.90$

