**Table 6. Stopping boundaries for CRc rate**

Stop accrual if the number with overall response is less than or equal to indicated (i.e., #
--

patients with overall response) among the number of patients evaluated				
Number of patients evaluated for CRc	5	10	15	20
Number of patients with CRc (i.e., CR, CRp, or CRi) is less than or equal to	0	0-1	0-2	Always stop with this many patients

The monitoring rule for the toxicity rate, based on these assumptions and monitoring conditions above is found in **Table 7**. For example, accrual will cease if 4 or more patients experience toxicities among the first 5 patients.

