**Table 7. Stopping boundaries for Toxicity**

Stop accrual if the number of drug-related non-hematological grade 3/4 toxicities is greater than or equal to indicated (i.e., # patients with toxicities) among the number of patients evaluated				
# patients evaluated	5	10	15	20
# patients with toxicities	4-5	6-10	8-15	Always stop with this many patients

Multc Lean Desktop (version 2.1.0) was used to generate the toxicity and futility stopping boundaries and the OC table (Table 8). In order to utilize the software for the design, a 20.0% ORR and beta (0.4, 1.6) priors were assumed for the standard treatment response distribution and experimental treatment response prior distribution, respectively. In addition, a 30% toxicity constant rate and beta (0.6, 1.4) priors were assumed for the standard treatment toxicity constant rate and experimental treatment toxicity prior distribution, respectively.

The probability of stopping the study early if the true ORR of the combination treatment was 35% and the true toxicity rate was 30% was 23.8%. Probabilities of stopping early for high true toxicity rates (i.e., 50%) were 63.3% when the true ORR was 35% and 57.5% when true ORR rate was 50%.

Table 8. Operating characteristics for simultaneous monitoring response and toxicity rates for patients treated with combination treatment		
True Toxicity Rate	True ORR	Prob(stop the trial early)
0.10	0.20	0.5391
	0.25	0.3835
	0.35	0.1686
	0.45	0.0642
	0.50	0.0378
0.20	0.20	0.5450
	0.25	0.3913
	0.35	0.1791

Table 8. Operating characteristics for simultaneous monitoring response and toxicity rates for patients treated with combination treatment		
True Toxicity Rate	True ORR	Prob(stop the trial early)
	0.45	0.0760
	0.50	0.0499
0.30	0.20	0.5778
	0.25	0.4352
	0.35	0.2384
	0.45	0.1427
	0.50	0.1185
0.40	0.20	0.6650
	0.25	0.5519
	0.35	0.3957
	0.45	0.3198
	0.50	0.3006
0.50	0.20	0.7965
	0.25	0.7278
	0.35	0.6330
	0.45	0.5869
	0.50	0.5752

- **Cohort #2: Patients with relapsed FLT3-ITD and –D835 mutant AML (FLT3 inhibitor failure cohort)**

The historical data suggested a CRc rate of 10% for this population and the target CRc rate with selinexor ad sorafenib combination is 20%. Given this, we will stop enrollment into this cohort if the observed patients' data suggest that:

- 1)  $\Pr(\text{CR}_{cE} > \text{CR}_{cH} + 0.10 | \text{data}) < 0.025$
- 2)  $\Pr(\text{TOX}_E > 0.30 | \text{data}) > 0.875$

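### Section 11.3 bases the primary efficacy analysis on an undefined ORR instead of CRc, and its dropout rule can score an achieved CRc as a failure

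*Combined protocol and SAP*

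**What the plan says.** Section 1.1 sets the phase II primary objective as the CRc rate "within 3 months of treatment initiation". Section 11.2 states that "the primary endpoint is the achievement of CRc (CRc=CR/CRp/CRi) at any time during the first three cycles of therapy". The benchmarks are CRc rates too. For the FLT3 inhibitor naive cohort the plan writes "The historical data suggested a CRc rate of 20% for this population and the target CRc with selinexor and sorafenib combination is 35" per cent; for the FLT3 inhibitor failure cohort the rates are 10% historical and 20% target.

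Section 11.3, the only section that specifies the primary estimate, uses another term: "For the primary efficacy analysis, we will estimate the ORR for the combination treatment, along with the 95% confidence interval". Its next sentence reads "In addition, we will estimate composite CRc rate, partial response and marrow clearance rate within 3 months by FLT3 mutation". It then gives the dropout rule: "Patients who drop out of the study before completing all the cycles will be treated as" failures for the primary analysis.

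Three other places bear on the point. Section 8.0 defines CRc as a confirmed remission rate and has a sentence on responders that also mentions hematologic improvement and morphologic leukemia-free state. Section 8.8 scores best response over the first three cycles, or at time off study for patients who stop treatment sooner. Section 9.1.4 keeps patients who stop treatment on study unless they withdraw consent for follow-up, die or are lost.

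**The concern.** Three things in section 11.3 do not fit the rest of the plan.

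- **Label.** The primary analysis is of ORR, the primary endpoint is CRc, and ORR is not defined for this trial. If ORR were read to include partial remission or marrow clearance, the reported rate would be set against CRc benchmarks it does not match, and the comparison would favour the treatment.
- **Dropouts.** A patient who reaches CRc and then leaves the study is a responder under 8.8 and 11.2 and a failure under 11.3. The 11.3 rule is not limited to the three cycles of the primary endpoint, and section 5.3.1 plans up to 24 cycles.
- **Window and confirmation.** Sections 1.1 and 11.2 give different windows, and 11.3 does not say which governs the primary rate, nor whether the confirmation mentioned in 8.0 is required for it.

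These are single-arm cohorts of 20. If the numerator can be settled after the data are seen, the reported rate can move between target and historical value.

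**Working it through.** **1. Do the design figures depend on the label?** Inputs from section 11.2: looks at 5, 10 and 15 patients. Naive cohort (Tables 6 and 7): stop if CRc ≤0, ≤1, ≤2 or toxicity ≥4, ≥6, ≥8. Failure cohort (Tables 9 and 10): CRc never, 0, 0; toxicity ≥4, ≥5, ≥7. Response and toxicity are taken as independent, and binomial counts are enumerated exactly:

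P(stop early) = 1 − P(no futility stop) × P(no toxicity stop)

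- Naive, CRc 35%, toxicity 30%: 1 − 0.83187 × 0.91555 = 0.2384. Table 8 gives 0.2384.
- Failure, CRc 20%, toxicity 30%: 1 − 0.89263 × 0.80433 = 0.2820. Table 11 gives 0.2820.

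All 25 cells of Table 8 and all 25 of Table 11 agree to within 0.00005 when the column headed ORR is taken as the CRc rate. The futility boundaries also follow from the stated CRc rules: Beta(0.4, 1.6) with threshold 0.20 + 0.15, Beta(0.2, 1.8) with threshold 0.10 + 0.10, cutoff 0.025. Correcting the label therefore changes no design figure.

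**2. What does ORR mean in 11.3?** Set side by side:

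| Points to ORR = CRc | Leaves it open |
|---|---|
| 11.2 calls the CRc benchmark ORR: "a 20.0% ORR and beta (0.4, 1.6) priors were assumed for the standard treatment response distribution"; the 10% benchmark is treated the same way | 11.3 lists CRc after ORR, as an addition |
| Tables 6 and 9 have the header "Stop accrual if the number with overall response is less than or equal to indicated" over a row that counts CRc | 8.8 speaks of primary endpoints and lists CRc, PR and marrow clearance |
| | The responder sentence in 8.0 is ambiguous |

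The only study for which the documents report an ORR is the single-agent study in 2.2.2. There ORR = 5 CR + 2 CRi/p + 1 PR + 2 MLFS = 10/63 = 15.9%, while CR with or without full recovery = 7/63 = 11.1%. This shows only that the terms can differ; the ratio need not apply to the combination.

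**3. Effect of scoring responders as failures.** One patient in 20 is 1/20 = 5 points. Intervals are Clopper-Pearson 95%, an assumption because the plan names no method.

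| Cohort | CRc counted | Rate | 95% CI |
|---|---|---|---|
| Naive, at target | 7/20 | 35% | 15.4–59.2% |
| one recoded | 6/20 | 30% | 11.9–54.3% |
| three recoded | 4/20 | 20% (historical) | 5.7–43.7% |
| Failure, at target | 4/20 | 20% | 5.7–43.7% |
| one recoded | 3/20 | 15% | 3.2–37.9% |
| two recoded | 2/20 | 10% (historical) | 1.2–31.7% |

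**4. Do the two windows agree?** Three months is 365.25/4 = 91.3 days. Section 5.1 allows 28 ± 7 days per cycle, with an early start no sooner than day 21. Three cycles last 3 × 28 = 84 days as planned, 3 × 21 = 63 at the shortest, and 3 × 35 = 105 at the long end, more with permitted delays. With 35-day cycles, the cycle 3 day 28 marrow in 7.2.5 falls on study day 70 + 28 = 98, range 91 to 105. A CRc first seen then counts under 11.2, but under 1.1 only if found by about day 91.

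**The case against.** The strongest reply is that ORR is a slip. Section 11.2 uses the two terms for the same 20% and 10% benchmarks, the responder sentence in 8.0 can be read as requiring CRc, and the additional CRc estimate in 11.3 may be only a breakdown by FLT3 mutation. Section 11.3 also mentions ORR over the study period separately, which suggests that its first ORR is the window-limited measure of 8.8. It can also fairly be said that reproducing Tables 8 and 11 does not identify the endpoint, because the arithmetic is the same whatever the binary response is called. On dropouts, 9.1.4 keeps most patients who stop treatment on study, so transplant alone would not be a dropout. Scoring dropouts as failures is a recognised conservative convention, and the cycles meant may be only the first three. The recoding scenarios are hypothetical.

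Much of this stands. The slip is the likelier reading, the reproduction shows only that relabelling is free of design cost, and the number of patients affected may be small. The contradiction remains. Section 11.3 never says that ORR is CRc, does not limit the cycles to three, and makes no exception for an achieved response. Section 8.8 applies time off study to patients who discontinue treatment, which is not how 9.1.4 uses the idea, so who counts as a dropout is itself unsettled. The confirmation question is a missing detail rather than an error, and the verdict does not rest on it.

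**Conclusion.** The concern holds. Read literally, section 11.3 can produce a primary rate that is not the CRc rate of 1.1 and 11.2, or can score a patient with a CRc as a failure.

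The effect is nil if ORR is taken as CRc and no responder leaves the study. Otherwise it is 5 points per recoded responder in a full cohort of 20. Losing the whole planned gain would take three of 7 responders in the naive cohort or two of 4 in the failure cohort. Those counts are illustrations at the target rates; the documents give no basis for predicting them. As planned, the two windows differ little (84 against about 91 days), and they matter mainly when cycles are prolonged or delayed. The stopping rules are unaffected, because their boundaries count CRc explicitly. This should be fixed before analysis.

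**What to change.** Replace the primary-analysis and dropout sentences in 11.3 with text to this effect:

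> Primary efficacy analysis: CRc (CR + CRp + CRi, as defined in Section 8) achieved during the first three cycles, estimated for each phase II cohort with a 95% CI. Best response is scored per 8.8. Patients who leave without a CRc meeting the Section 8 definition count as non-responders. A CRc meeting that definition and reached before leaving for any reason, including HSCT, counts as a response.

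Then:

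- State one window and use it in both 1.1 and 11.2.
- Say whether the confirmation in 8.0 applies to the primary endpoint.
- Make ORR a secondary measure with listed components, or delete it.
- Replace ORR and overall response by CRc in the text of 11.2 and in Tables 6, 8, 9 and 11.

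The cost is wording only. Sample size, boundaries and operating characteristics do not change.

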#### 4.1 Inclusion Criteria

##### 4.1.1 Phase I

FLT3-ITD and/or FLT3-D835 mutated patients 18 years of age or older with relapsed/ refractory AML (any number of relapses) including patients who may have been previously exposed to one or more FLT3-inhibitor therapies will be eligible for the phase I portion of this study.

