## 11.0 STATISTICAL CONSIDERATIONS

The primary objectives of the study are to evaluate safety and efficacy of selinexor in combination with sorafenib in patients with FLT3-ITD and -D835 mutated AML. The total accrual is 52 patients (Phase I: up to 12 patients and Phase II: 20 patients per cohort).

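### Section 11.3 states no final response estimate for each phase II cohort: read literally, the primary efficacy analysis is one ORR in all treated patients, which matches neither cohort's CRc benchmark

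*Combined protocol and SAP*

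**What the plan says.** Section 11.3 defines the efficacy population as follows: "All patients who received any dose of the study agent will be included in the analysis for efficacy and safety". The primary analysis is one sentence: "For the primary efficacy analysis, we will estimate the ORR for the combination treatment, along with the 95% confidence interval". The next sentence gives the only breakdown of response rates: "In addition, we will estimate composite CRc rate, partial response and marrow clearance rate within 3 months by FLT3 mutation". No phase, dose level or cohort is named, and there is no comparison with a historical rate.

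Section 11.2 is built by cohort. The endpoint is given thus: "For all the cohorts, the primary endpoint is the achievement of CRc (CRc=CR/CRp/CRi) at any time during the first three cycles of therapy". Response and toxicity are monitored "separately for each cohort". The inhibitor-naive cohort has a historical CRc rate of 20% and a target of 35%; the inhibitor-failure cohort has 10% and 20%. Each has its own prior, stopping boundaries and operating characteristics (Tables 6 to 11).

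Section 11.0 gives the accrual of 52 as "Phase I: up to 12 patients and Phase II: 20 patients per cohort". Section 4.1.1 admits to phase I patients with "relapsed/ refractory AML (any number of relapses", whereas both phase II cohorts are limited to two prior salvage regimens (3.1, 4.1.3). Table 3 lists selinexor levels from 40 to 100 mg twice weekly for phase I. CRc is the primary objective in phase II (1.1) and a secondary one in phase I (1.2).

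**The concern.** The cohorts are defined by prior FLT3-inhibitor exposure, and FLT3 mutation type is a different variable. The one split in 11.3 therefore does not recover the cohorts. The phrase on separate cohorts in 11.2 governs monitoring, and Tables 6 and 9 hold only futility boundaries at 5, 10 and 15 patients. At 20 patients they close accrual without an efficacy criterion. The estimate in 11.3 is thus the only final efficacy result that the plan specifies.

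If 11.3 is followed as written, that result answers neither phase II question. It also mixes in phase I patients who differ in prior treatment and dose. If a per-cohort analysis is intended but unstated, the choice between an overall and a per-cohort rate stays open until the data have been seen.

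The measure is a second difficulty. Section 11.3 estimates ORR, while the benchmarks are CRc rates. Section 11.2 seems to use the two terms interchangeably in its operating characteristics, but the description of responders in section 8.0 is not clearly limited to CRc. In the background results for selinexor alone (2.2.2) the two differ: ORR was 10/63 (16%), and CR with or without full recovery was 7/63 (11%).

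**Working it through.** **1. Is the design per cohort?** Boundaries follow from beta-binomial posteriors at n = 5, 10 and 15, using the priors Beta(0.4, 1.6) and Beta(0.2, 1.8) for response and Beta(0.6, 1.4) for toxicity. The futility thresholds are 0.20 + 0.15 = 0.35 (naive) and 0.10 + 0.10 = 0.20 (failure), with cut-off 0.025. The toxicity limit is 0.30, with cut-offs 0.90 (naive) and 0.875 (failure).

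- Naive: stop for futility at ≤0, ≤1, ≤2 responses; for toxicity at ≥4, ≥6, ≥8. This matches Tables 6 and 7.
- Failure: futility never, 0, 0; toxicity ≥4, ≥5, ≥7. This matches Tables 9 and 10.

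P(stop early) = 1 − P(no futility stop) × P(no toxicity stop), with response and toxicity independent:

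- Naive, response 35%, toxicity 30%: 1 − 0.8319 × 0.9156 = 0.238 (Table 8: 0.2384).
- Failure, response 20%, toxicity 30%: 1 − 0.8926 × 0.8043 = 0.282 (Table 11: 0.2820).

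All 50 cells of Tables 8 and 11 reproduce to four decimals. The design works cohort by cohort.

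**2. What would an overall rate estimate?** Expected rate = (12·pI + 20·pN + 20·pF)/52, where pI, pN and pF are the phase I, naive and failure rates. The documents do not give the phase I mix, so pI is assumed to lie between pF and pN.

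| Truth | pI = pF | pI = pN |
|---|---|---|
| Both at benchmark (20%, 10%) | 7.2/52 = 13.8% | 8.4/52 = 16.2% |
| Both at target (35%, 20%) | 13.4/52 = 25.8% | 15.2/52 = 29.2% |
| Only naive at target (35%, 10%) | 10.2/52 = 19.6% | 13.2/52 = 25.4% |
| Only failure at target (20%, 20%) | 10.4/52 = 20.0% | 10.4/52 = 20.0% |

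The last two rows overlap: success in one cohort only looks much the same whichever cohort it is.

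**3. Is the mix fixed?** No. At target response and 30% toxicity, the chance that at least one cohort stops early is 1 − 0.7616 × 0.7180 = 45%, taking the cohorts as independent. If the failure cohort stopped at 10 patients, the overall rate with both cohorts at benchmark would be (12·pI + 4 + 1)/42, or 14.8% to 17.6%. If the naive cohort stopped at 10, it would be (12·pI + 2 + 2)/42, or 12.4% to 15.2%.

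**4. One overall result, two opposite readings.** Take 12/52 = 23.1% (exact 95% CI 12.5% to 36.8%), with 2 responders in phase I. Both splits below can occur without crossing the futility boundaries.

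| Naive | Exact 95% CI | Failure | Exact 95% CI | Lower limit above benchmark |
|---|---|---|---|---|
| 9/20 | 23.1% to 68.5% | 1/20 | 0.1% to 24.9% | naive only (20%) |
| 4/20 | 5.7% to 43.7% | 6/20 | 11.9% to 54.3% | failure only (10%) |

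**5. What does a per-cohort interval at n = 20 deliver?**

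- Naive: the lower limit exceeds 20% from 9/20 on. P(X ≥ 9) is 0.010 at a true rate of 20% and 0.238 at 35%.
- Failure: the lower limit exceeds 10% from 6/20 on. P(X ≥ 6) is 0.011 at 10% and 0.196 at 20%.

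**The case against.** The strongest reply is that combining the groups is inferred from silence. Section 11.3 never says that phases or cohorts are merged; its wording can be read as naming the regimen and setting a treated-patient rule. Much of the plan points to a per-cohort phase II analysis: CRc is primary only in phase II, the endpoint is set for all the cohorts, each cohort has its own benchmark and boundaries, and for the naive cohort 11.2 says what increase would merit further study. This stands as evidence of intent. It does not supply the missing statement, because none of these places says how the final estimate is grouped or whether phase I patients enter it.

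A reader might also infer that neither benchmark can be judged at all. That goes too far. At 5, 10 and 15 patients each cohort is checked against its own benchmark plus margin, and cohort results could be tabulated at the end. The gap is in the stated final analysis.

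A third reply is that a per-cohort interval at 20 patients is too wide to settle the benchmark question. Step 5 bears this out. It limits what the estimate can claim, but does not favour an overall rate, which addresses a different quantity.

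**Conclusion.** The point holds as a gap in the stated primary analysis. Taken literally, 11.3 yields one ORR in all treated patients, and no final analysis sets either cohort's CRc rate beside its benchmark. The overall rate would be expected at 13.8% to 16.2% with both cohorts at benchmark and 25.8% to 29.2% with both at target. These ranges assume full accrual of 12 + 20 + 20 and a phase I rate between the two cohort rates. The 12/52 example further assumes 2 phase I responders.

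Three stronger readings are not supported. The plan does not declare that it combines the groups. An even average of the cohort figures (15.0% at benchmark, 27.5% at target) is not the rate that the literal text implies, because it leaves out phase I. Nor do the documents show that prior inhibitor exposure confounds the association tests in 11.3; that would require it to be related to the characteristic tested as well as to response.

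Sample size and stopping boundaries are unaffected.

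**What to change.** Amend 11.3 as follows.

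- The primary efficacy analysis is the CRc rate within the first three cycles (not ORR), with an exact 95% confidence interval, separately for the inhibitor-naive and inhibitor-failure phase II cohorts, each set beside its own benchmark and target.
- Name the cohorts by population. Cohort 1 is the inhibitor-failure cohort in 3.1 and 4.1.3 but the inhibitor-naive cohort in 11.2, so a number alone could attach the wrong benchmark.
- Report phase I response separately by dose level. State in advance whether phase I patients treated at the RP2D enter any supportive estimate.
- Label any overall rate descriptive.

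The cost is SAP wording and wider intervals: 4/20, for example, gives 5.7% to 43.7%. At the target rate the lower limit clears the benchmark with a probability of only about 24% (naive) and 20% (failure). The result should therefore be presented as estimation and not as a test.

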### **1.2 Secondary Objectives**

#### **Phase I**

1. To determine the composite CRc rate including CR + CRp + CRi within 3 months of treatment initiation in FLT3-ITD and –D835 mutated patients with relapsed/ refractory AML.
2. To determine the partial response (PR), marrow clearance rate, bone marrow blast reduction  $\geq 50\%$  within 3 months of treatment initiation in FLT3-ITD and –D835 mutated patients with relapsed/ refractory AML.
3. To determine the duration of response (DOR), event-free survival (EFS), overall survival (OS), and number of patients bridged to hematopoietic stem cell transplant (HSCT) and median duration to HSCT from the initiation of the combination of selinexor with sorafenib in FLT3-ITD and –D835 mutated patients with relapsed/ refractory AML.
4. To determine the safety of the combination of selinexor with sorafenib in FLT3-ITD and –D835 mutated patients with relapsed/ refractory AML.

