#### **Phase II**

1. To determine the PR, marrow clearance rate, bone marrow blast reduction  $\geq 50\%$  within 3 months of treatment initiation in FLT3-ITD and –D835 mutated patients with relapsed/ refractory AML.
2. To determine the DOR, EFS, OS, and number of patients bridged to HSCT and median duration to HSCT from the initiation of the combination of selinexor with sorafenib in FLT3-ITD and –D835 mutated patients with relapsed/ refractory AML.
3. To determine the safety of the combination of selinexor with sorafenib in FLT3-ITD and –D835 mutated patients with relapsed/ refractory AML.

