### **1.3 Exploratory Objectives**

1. To evaluate the response rate, EFS and OS in FLT3 mutated/NPM1 wild-type patients versus FLT3 mutated/NPM1 mutated versus FLT3 wild-type/NPM1 mutated patients treated with the combination of selinexor and sorafenib.
2. Quantitative changes of FLT3-ITD and –D835 allelic burden with time in patients treated with the combination of selinexor and sorafenib.
3. To evaluate the extent of pharmacodynamics biomarker (such as p-FLT3, p-p70S6K, pERK) inhibition and the induction of apoptosis in the bone marrow and peripheral blasts following treatment with the combination of selinexor and sorafenib.
4. To investigate possible relationships between selinexor and other baseline gene expression signatures and clinical response.
5. To store and/or analyze surplus blood or tissue including bone marrow, if available, for potential future exploratory research into factors that may influence development of AML and/or response to selinexor (where response is defined broadly to include efficacy, tolerability or safety).
6. To evaluate the pharmacodynamic effects of treatment on induction/inhibition of XPO1 using qRT-PCR and on plasma protein/cytokine levels.

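### Section 11.3 has no analysis that matches the EFS objective, and it summarises duration of response without any handling of censoring

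*Combined protocol and SAP*

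**What the plan says.** Section 1.2 sets the secondary objectives. For Phase II: "To determine the DOR, EFS, OS, and number of patients bridged to HSCT and median duration to HSCT". The Phase I list contains the same endpoints. Exploratory objective 1 in section 1.3 uses EFS again: "To evaluate the response rate, EFS and OS in FLT3 mutated/NPM1 wild-type patients", compared with two other FLT3/NPM1 groups.

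Section 11.3 is the only analysis text for these endpoints. Its time-to-event sentence reads: "The distribution of time-to-event endpoints (DFS and OS) including overall survival and progression free survival will be estimated". The method named there is Kaplan-Meier. DOR is not in that sentence. It appears earlier in the same section: "Demographic/clinical characteristics (including duration of response) and safety data of the patients will be summarized using descriptive statistics such as mean, standard deviation, median and" (the list closes with the range).

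On definitions, section 8.7 defines relapse after CR and after PR. No section gives a start date, event list or censoring rule for EFS, DFS, PFS or DOR.

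**The concern.** Two things do not fit together. First, the endpoints named in the objectives and those named in the analysis plan agree only on OS. EFS, DFS and PFS are distinct measures in ordinary use, and the plan defines none of them. The curve that eventually answers the EFS objective could therefore be settled after the data are seen.

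Second, DOR is a time-to-event endpoint, but it is placed among summaries for fully observed variables. Some responses will still be ongoing, or will have been cut off, at analysis. Section 2.1 reports 20-30% of patients on FLT3 inhibitors bridged to transplant, and section 5.3.1 allows 24 cycles or more for patients who benefit. Section 2.3 argues that selinexor may lengthen the 3-6 month responses seen with FLT3 inhibitors. DOR is the endpoint that speaks to that claim, and a downward bias could hide the effect the trial hopes to see.

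**Working it through.** **Step 1: objectives against analysis.**

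| Endpoint | In the objectives (1.2, 1.3) | Analysis in 11.3 | Defined |
|---|---|---|---|
| OS | yes | Kaplan-Meier | name is self-explanatory |
| EFS | yes (both phases, exploratory 1) | none named | no |
| DOR | yes (both phases) | descriptive statistics | no |
| DFS | no | Kaplan-Meier | no |
| PFS | no | Kaplan-Meier | no |

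The documents give no event count, power or precision for any of these endpoints, so there is no planned figure to reproduce.

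**Step 2: effect of ignoring censoring on the DOR median.** This is an illustration. The 3-6 month range and the 20-30% transplant share come from section 2.1. The midpoint of 4.5 months, the exponential shape, all follow-up times, the timing of transplant and the act of censoring at transplant are assumptions.

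Let the true DOR have median m, so S(t) = exp(-ln 2 × t / m). Let G(t) be the probability of still being uncensored at t, with censoring independent of DOR. A plain median of the observed times is the t that solves S(t) × G(t) = 0.5. It equals m only if no censoring occurs before m.

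With a share f censored at transplant, uniformly over 1-3 months, and the rest followed for a uniform 2-12 months, for t between 2 and 3:

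G(t) = f × (3 - t)/2 + (1 - f) × (12 - t)/10

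For m = 4.5:

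- f = 0.20, t = 2.75: S = 0.655; G = 0.20 × 0.125 + 0.80 × 0.925 = 0.765; product 0.50.
- f = 0.30, t = 2.52: S = 0.678; G = 0.30 × 0.24 + 0.70 × 0.948 = 0.736; product 0.50.
- f = 0, t = 3.47: S = 0.586; G = (12 - 3.47)/10 = 0.853; product 0.50.
- f = 0, follow-up 12-60 months, t = 4.5: S = 0.50; G = 1; product 0.50.

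| Assumed censoring | Plain median (true 4.5 months) | Shortfall |
|---|---|---|
| 20-30% at transplant, rest followed 2-12 months | 2.5-2.8 | 39-44% |
| None at transplant, 2-12 months | 3.5 | 23% |
| 20-30% at transplant, rest followed 12-60 months | 2.65-3.05 | 32-41% |
| None at transplant, 12-60 months | 4.5 | none |

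For true medians of 3 and 6 months, the first row becomes 2.1-2.3 and 2.7-3.1 months, and the last row becomes 3.0 and 6.0. A Kaplan-Meier median targets the true value in every row, because censoring is independent here by assumption.

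**Step 3: the other reading of the DOR sentence.** If only responses that have ended are summarised, the first-row assumptions give a median of 2.0-2.2 months against 4.5. That is also low.

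**Step 4: number of patients behind DOR.** At the target CRc rates in 11.2, 20 × 0.35 = 7 responders are expected in the inhibitor-naive cohort and 20 × 0.20 = 4 in the inhibitor-failure cohort.

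**The case against.** The best defence is that DFS or PFS is simply a loose label for EFS. That may be so, but with none of the three defined the documents cannot confirm it. What stands is a mismatch of undefined labels.

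A reader might go further and infer that EFS is replaced by a curve in responders only, dropping 65% of the inhibitor-naive cohort (13 of 20) and 80% of the inhibitor-failure cohort (16 of 20) even at the target CRc rates. The documents do not support this. Those figures hold only if DFS is read as starting at remission, which the plan nowhere says. Section 11.3 also plans a PFS curve, and it opens by including every patient who received any study drug in the efficacy analysis.

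A reader might also infer that 11.3 treats every response as ended. It does not say so. It is silent on ongoing responses, and its list of statistics is open-ended and includes the median. None of the listed statistics handles censoring, however, and no rule is supplied elsewhere.

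The strongest quantitative objection is that the DOR bias is not inevitable. No text censors DOR at transplant, and section 7.2.12 follows responders for up to 5 years. With long, complete follow-up and no transplant censoring the bias disappears, as the last row of the table shows. That stands, and it is why the result is given as a range. Against it, the 7.2.12 follow-up is described as being for survival and may be by telephone, so relapse-free follow-up of that length is not assured.

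Finally, these are secondary endpoints in small single-arm cohorts. No stopping rule or primary conclusion depends on them.

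**Conclusion.** The concern holds in this form. As written, section 11.3 contains no analysis that matches the EFS objective. It assigns Kaplan-Meier to two endpoints outside the objectives, and it summarises DOR by statistics that take no account of censoring. The first part rests on the text alone. The size of the second depends on follow-up and transplant handling: for an assumed true median of 4.5 months, the plain median runs from 2.5 months (44% low) to 4.5 months (no bias). The direction is downward whenever responses are ongoing, cut off at last contact or censored at transplant. The point should be corrected before analysis, but it does not threaten the primary endpoint.

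**What to change.** In section 11.3:

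- Replace DFS and PFS with EFS and DOR, both by Kaplan-Meier alongside OS. Remove DOR from the descriptive-statistics sentence.
- **EFS:** all treated patients, from first dose to the earliest of failure to reach CRc by the end of the primary window, relapse per 8.7, or death. Write into 11.3 the date assigned to the failure event. State the window once, since 1.1 gives it as 3 months and 8.8 and 11.2 as three cycles.
- **DOR:** patients with CRc, from first documented response to relapse per 8.7 or death, with ongoing responders censored at the last disease assessment. Report PR separately, if at all. Say that the 8.7 rule for relapse after CR also covers CRp and CRi. Naming the population matters because section 8.0 also mentions hematologic improvement and morphologic leukemia-free state in describing responders.
- **Transplant:** state one rule for the main analysis of each endpoint, for example not censored, and report the alternative as a sensitivity analysis.

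The cost is mostly wording. Relapse status must also be recorded at the post-treatment contacts in 7.2.12, which are now described only as survival follow-up. The EFS curve may look less favourable than the curves now named. With about 7 and 4 responders expected at target, the DOR estimates will be imprecise under any method.
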